1.1 SYNOPSIS	
Title:	Development and validation of a digital pain-reduction kit for musculoskeletal injuries
Study Description:	This study will test the effectiveness of an evidence-based, multi-modal, "digital pain-reduction kit" as a non-pharmacological supplement to managing patients with pain due to musculoskeletal injuries. Outpatients will be randomized to receive either the pain reduction kit or an active control. The kit will contain a virtual reality (VR) headset, therapeutic VR visualization software, a low-cost wearable transcutaneous electrical nerve stimulation (TENS) unit. The control group will receive a TENS unit; they will not receive VR, or remote coaching. Study devices will be delivered to the patient's home with instructions for use; patients will receive remote clinical and technical support. Patients will be followed for 60 days and monitored for functional status, pain levels, use of pain medications (including opioids), satisfaction with care, and time to returning to work. Participants will also be asked to consent/authorization to access medical records from their treating facility (if a non-CSMC site).
Objectives:	Primary Objective: The primary objective of this study is to develop and validate a multi-modal digital pain reduction kit for improving physical function over time. Secondary Objective: The secondary objective of this study is to investigate the efficacy of a multi-modal digital pain reduction kit in reducing pain interference over time, work productivity, opioid use, and satisfaction with care.
Endpoints:	Primary Endpoint: The primary outcome measures in this study are weekly surveys (PROMIS® PF short-form) of self-reported physical function. Secondary Endpoints: The secondary outcome measures in this study are pain interference (PROMIS® Pain Interference), work absenteeism and presenteeism (WPAI:LB), number of 90 Morphine Milligram Equivalent opioid prescriptions, and satisfaction with healthcare (Pain Treatment Satisfaction Scale and SF Patient-Satisfaction Questionnaire).
Study Population:	The study consists of 174 English adults (75 intervention; 75 control with TENS; 24 control without TENS) in the Greater Los Angeles Area presenting with pain from musculoskeletal injuries.
Phase:	N/A
Description of	Cedars-Sinai Medical Center Orthopedic Clinic
Sites/Facilities Enrolling	Cedars-Sinai Medical Delivery Network (MDN)
Participants:	Medical College of Wisconsin (MCW)

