3 OBJECTIVES AND ENDPOINTS

OBJECTIVES	ENDPOINTS	JUSTIFICATION FOR ENDPOINTS
Primary		
The primary objective of this study is to develop and validate a multi- modal digital pain reduction kit for improving physical function over time.	The primary endpoint in this study is a clinically significant change in self- reported physical function over time among individuals in the intervention arm compared to those in the active control. The outcome measure used to quantify this endpoint is the PROMIS® PF short-form, a validated self-report of physical function. The	The PROMIS® PF short- form scale is a widely validated instrument with excellent content validity, construct validity, and reliability in patients with spinal disorders and other conditions marked by

OBJECTIVES	ENDPOINTS	JUSTIFICATION FOR ENDPOINTS
	outcome measure is administered on a weekly basis via a smartphone survey to capture longitudinal change and variation among participants.	diminished mobility. The outcome measure allows us to place patients on a continuum of physical function with respect to various physical actions.
Secondary		
The secondary objective of this study is to investigate the efficacy of a multi-modal digital pain reduction kit in reducing pain interference over time, work productivity, opioid use, and satisfaction with care.	The secondary endpoints of are clinically significant changes in pain interference, work productivity, use of opioids, and satisfaction with healthcare among those in the intervention arm compared to participants in the active control. Outcome measures include pain interference (PROMIS® Pain Interference, measured weekly via smartphone surveys), work absenteeism and presenteeism (WPAI:LB, measured at baseline and exit surveys), number of 90 Morphine Milligram Equivalent opioid prescriptions (obtained via cumulative EHR records), and satisfaction with healthcare (CG- CAHPS, measured once at the conclusion of the study).	
Tertiary/Exploratory		
N/A	N/A	N/A

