4 STUDY DESIGN

4.1 OVERALL DESIGN

This RCT will enroll 174 patients with pain due to musculoskeletal injuries to test the efficacy of a multi- model digital pain reduction kit on short term pain management as an adjunct to traditional medical therapy. We will attempt to enroll a minimum of 90 patients reporting lower back pain specifically, as patients without lower back pain are less likely to use the TENS unit. Prior to adding the TENS unit to the control arm, we recruited 24 control patients. However, we will not discard their data since we intend on performing a supplementary sensitivity analysis. In addition to these 24 controls, we will randomize 75 patients to receive the study intervention (multi-modal digital pain-reduction kit with optional remote coaching support), and the other 75 patients will receive an active control. We will allocate patients using a random number generator to ensure that there is an equal distribution of participants in the control vs. experimental group. The primary outcome will be changes in self-reported physical function measured by the Patient Reported Outcome Measurement Information System (PROMIS®) Physical Function Scale. Secondary outcomes will include PROMIS® Pain Interference Scale, PROMIS® Global Health Scale, work productivity and activity impairment questionnaire (WPAI) (for patients with lower back pain specifically), patient satisfaction measured by the Pain Treatment Satisfaction Scale and SF Patient-Satisfaction Questionnaire), and use of opioids (measure in morphine milligram equivalents).

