To collect the patient reported outcomes (PROs) for this study, we will use ecological momentary assessment (EMA) software (LifeData), a HIPAA-compliant, cloud-based survey administration platform capable of administering surveys in real-time. We will also allow patients use Redcap as an alternative program to collect PROs. With this program the patient doesn't have to use an app on their phone and instead just respond to surveys sent to their email address. To administer PROs, we will upload a list of patient email addresses into their HIPAA-compliant website which in turn allows scheduled administration of PRO questionnaires at daily and weekly intervals. Each week, the EMA app will send patients a reminder to fill out the scheduled PROs. If they do not fill them out, they will be sent a reminder prompt. The data collected by LifeData or Redcap will then be downloaded into a secure analysis and visualization file accessible to the research team and the Digitalist.

Work Productivity and Activity Impairment

Work productivity can be measured in terms of absenteeism (missing work) and presenteeism (diminished productivity at work). The Work Productivity and Activity Impairment (WPAI) questionnaire is a validated, widely used, brief, 6-item questionnaire that measures absenteeism and presenteeism related to specific health conditions.

Use of Opioids

In order to capture medication use related to their injury, including the use of opioids, we will link patient electronic health record (EHR) data to the other data sources using Medical Record Numbers and date of birth. We will collect opioid prescription information using pharmaceutical claims data, and also collect information on medications commonly used by individuals with chronic pain conditions. Prescribed opioid medications include: codeine, dihydrocodeine, tramadol, morphine, hydromorphone, oxymorphone, tapentadol, buprenorphine, methadone, oxycodone, fentanyl, remifentanil. We will convert all opioid doses into a single metric using morphine milligram equivalents (MME).

Satisfaction with Pain Treatment and Healthcare Surveys

We will evaluate patient experience data as measured by the 39-item Pain Treatment Satisfaction Scale and the 18-item short-form version of the Patient-Satisfaction Questionnaire. Both questionnaires are validated for use in studies to compare patient satisfaction between different treatment assignments.

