9 STATISTICAL CONSIDERATIONS

9.1 STATISTICAL HYPOTHESES

• Primary Efficacy Endpoint(s):

Primary Outcome: Physical function over time as measured by PROMIS PF score (T- Scored, Continuous)

Question: Which intervention is more effective in improving physical function?

Independent variable of interest: Comparator received, intervention vs. control (Dichotomous)

Potential Covariates: Age, gender, race, ethnicity, mental health comorbidities, chronic pain diagnosis, use of other pain medications (neuropathic pain medications, NSAIDS, antidepressants), benzodiazepine use, number of office visits during study period, baseline PROMIS[®] scores, encounter month, physician years of practice, physician gender.

• Secondary Efficacy Endpoint(s):

Secondary Outcome: Pain over time as measured by PROMIS Pain Interference Score (T-Scored, Continuous)

Question: Which intervention is more effective in improving patient's pain interference?

Independent variable of interest: Comparator received, intervention vs. control (Dichotomous).

Potential Covariates: Same as Primary Aim.

Secondary Outcome: Effects of lower back pain symptom severity on work productivity and regular activities over time as measured by WPAI:LB (T-Scored, Continuous).

Question: Which intervention is more effective in improving patient's work productivity and participation in regular activities?

Independent variable of interest: Comparator received, intervention vs. control (Dichotomous).

Potential Covariates: Same as Primary Aim.

Secondary Outcome: New Opioid Prescription over 90MME (Dichotomous)

Question: Which intervention is more effective in reducing opioid prescriptions of 90 Morphine Milligram Equivalents (MME) or greater?

Independent variable of interest: Comparator received, intervention vs. control (Dichotomous).

Potential Covariates: Same as Primary Aim.

Statistical Analyses: As in the primary aim analyses, we will employ mixed effects models featuring both fixed effects and random effects to account for within subject variation.

Because this particular outcome is binary, we will use mixed logistic regressions in which the log odds of the outcomes are modeled as a linear combination of the predictors.

Secondary Outcome: Satisfaction with Pain Treatment and Healthcare Scores

Question: Which intervention is more effective in improving how satisfied patients feel with their care?

Dependent variable: Pain Treatment and Patient Satisfaction Scores

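### The opioid endpoint is defined inconsistently across sections, and the mixed logistic model named for it has no stated repeated binary outcome to support its random effect

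*Combined protocol and SAP*

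**What the plan says.** The opioid outcome is a secondary endpoint of the combined protocol and SAP. It is described in five places.

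- **Section 1.1 (Synopsis):** "number of 90 Morphine Milligram Equivalent opioid prescriptions".
- **Section 3:** the same count, "obtained via cumulative EHR records".
- **Section 4.1:** "use of opioids (measure in morphine milligram equivalents".
- **Section 8.1:** "We will convert all opioid doses into a single metric using morphine milligram equivalents (MME". This section links health-record data but takes the opioid prescription information from pharmaceutical claims.
- **Section 9.1:** the outcome is "New Opioid Prescription over 90MME (Dichotomous", whereas the question beneath it concerns "reducing opioid prescriptions of 90 Morphine Milligram Equivalents (MME) or greater".

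For the model, Section 9.1 says "we will use mixed logistic regressions in which the log odds of the outcomes are modeled" and gives within-participant variation as the reason for random effects. The covariates are labelled potential and are those of the primary aim. The schedule of activities (Section 1.3) collects opioid data from the health record on Day 1 and at the Day 60 visit only. Section 9.4.3 does not name the opioid endpoint.

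**The concern.** A count, an amount and a yes/no event are different outcomes. They need different models and can lead to different conclusions about the same patients. The trial is unblinded (Section 6.2), so a definition left open until analysis could be chosen with the results in view.

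The model raises a separate problem. A random intercept separates variation between participants from variation within them, which requires more than one outcome value per participant. A new-prescription indicator drawn from cumulative records naturally yields one value each. A long covariate list with no selection rule adds to the difficulty, because the adjusted estimate then depends on choices the plan does not make.

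**Working it through.** The plan states no event rate, effect size or power for this endpoint, so there is no figure of its own to reproduce. The sample size in Section 9.2 concerns physical function only.

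**Step 1. Definitions side by side**

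| Section | Form | Threshold | Must be new? | Source |
|---|---|---|---|---|
| 1.1 | count | 90 MME | not stated | not stated |
| 3 | count | 90 MME | not stated | cumulative health records |
| 4.1 | use in MME | none | not stated | not stated |
| 8.1 | doses converted to MME | none | not stated | claims, with linked health records |
| 9.1, outcome | yes/no | above 90 | yes | not stated |
| 9.1, question | prescriptions | 90 or more | not stated | not stated |

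The two thresholds in Section 9.1 classify a prescription of exactly 90 MME differently. The two wordings also treat a continuing prescription differently. No section says whether 90 MME is a daily dose or a total per prescription. A prescription that reaches 90 MME per day also reaches it in total, but the converse need not hold, so the time basis could change the event frequency considerably.

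**Step 2. The random intercept**

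With one yes/no per participant, the model is logit P(Y_i = 1 | u_i) = β0 + β1·arm_i + u_i, with u_i normal with variance σ².

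- With arm alone, the data supply two proportions, one per arm.
- The model has three unknowns: β0, β1 and σ.
- For any σ, some β0 and β1 reproduce both proportions exactly. So σ is not identified, and the value of β1 depends on the σ assumed.
- Baseline covariates do not help, because they add no within-participant information. Any apparent identification would come from the assumed shape of the model.

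This result does not depend on the event rate. If the Day 1 and Day 60 collections were instead treated as two records per participant, two binary values would identify σ only weakly. Dated prescriptions would be another possible unit. The plan states none of these.

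**Step 3. Size of the full covariate list**

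Inputs:

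- The Section 9.1 list has 4 demographic items, 2 diagnoses, 2 medication items, office visits, baseline PROMIS scores, encounter month and 2 physician items: 4 + 2 + 2 + 1 + 1 + 1 + 2 = 13.
- With arm, and one parameter per item, that is 13 + 1 = 14. Multi-level coding of race, medication class or month would raise it.
- N = 75 + 75 = 150 without the 24 controls who had no TENS unit, and 150 + 24 = 174 with them (Sections 4.1 and 6.2).

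Events per parameter = min(events, non-events) / 14. The rates below are assumptions.

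| Assumed rate | N = 150 | N = 174 |
|---|---|---|
| 5% | 7.5/14 = 0.54 | 8.7/14 = 0.62 |
| 10% | 15/14 = 1.07 | 17.4/14 = 1.24 |
| 20% | 30/14 = 2.14 | 34.8/14 = 2.49 |
| 30% | 45/14 = 3.21 | 52.2/14 = 3.73 |
| 50% (maximum) | 75/14 = 5.36 | 87/14 = 6.21 |

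The last row is a ceiling that no event rate can exceed. Even at the total of 245 in Section 9.2, the ceiling is 122.5/14 = 8.75.

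**Step 4. Timing of covariates**

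The number of office visits made while the study is running is a post-randomization quantity that treatment could affect. No time point is given for the use of other pain medications.

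**The case against.** **Section 9.1 governs.** It is the only statistical text that gives a variable type and a model for this endpoint, and both are binary. The MME wording in Section 4.1 may only name a unit, and the conversion in Section 8.1 is needed before any 90-MME threshold can be applied. This is a fair reading and could reduce three forms to two. It does not remove the conflict between count and yes/no, and Section 9.1 disagrees with itself on the threshold and on whether the prescription must be new.

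**The plan does not commit to 13 covariates.** This stands. They are labelled potential, so the events-per-parameter ceiling describes a model the plan permits, not one it requires. The defect is the missing selection rule.

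**The unit of analysis is unstated, so repeated records are possible.** This also stands. For the same reason, it cannot be said that a pre-treatment Day 1 record would be averaged into the arm effect, since the plan nowhere says that Day 1 and Day 60 are stacked. But a model whose stated purpose is to handle repeated outcomes should say what those outcomes are.

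**The endpoint is secondary and was never powered.** Agreed. Low power here is not an error in the plan and forms no part of this point.

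**Conclusion.** The point holds in two parts that need no assumed figure. First, the opioid endpoint has conflicting definitions in form, threshold, the requirement to be new, and source, and its MME time basis is missing. Second, the mixed logistic model has no stated repeated binary outcome. On the natural reading of one cumulative yes/no per participant, a participant-level random intercept is not identifiable.

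A third part is conditional. If the full covariate list were used, there would be at most about 5 to 6 events per parameter at N = 150 to 174, with one parameter per covariate, and fewer with finer coding.

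A reader might infer that the event is rare and that no logistic model could be fitted reliably. The documents do not support this. They give no event rate, leave the 90-MME time basis open and do not require every covariate. At moderate event rates with simple coding, an ordinary logistic regression may well converge.

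The matter affects a stated secondary objective and should be settled before analysis. It does not touch the primary endpoint.

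**What to change.** 1. Choose one endpoint definition, stating its form, threshold, whether 90 MME is per day or per prescription, what counts as new for someone already taking opioids, the data source, and the Day 1 to Day 60 window. Use it in the synopsis and in Sections 3, 4.1, 8.1 and 9.1.
2. If the binary form is kept, analyse one row per participant by ordinary or Firth-penalised logistic regression without a random effect. Include arm and a short pre-specified baseline set, such as Day 1 opioid use, which the schedule already collects. Exclude post-randomization covariates. If a count or an amount is chosen instead, name a model to match.
3. Total MME over the window can serve as a supportive measure, but it must be defined. Section 8.1 converts doses and states neither a total nor a window.
4. State the expected event rate, or say that it is unknown.

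The cost is mainly SAP and protocol wording, with no added visits or questionnaires. Whether any further data are needed depends on which source is chosen and whether it is already being obtained. The small downside is fewer adjustment covariates for this endpoint.

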9.2 SAMPLE SIZE DETERMINATION

We will power this study to detected a 0.6 standard deviation (SD) effect size in PROMIS® PF scores between arms – a value that is three-times the established minimal clinical important difference of 0.2 SD and is considered a "moderate effect" using the

rules of Cohen. Assuming an 80% power, a level of 0.05, and a 25% withdrawal rate, we calculate a minimal

sample size requirement of approximately 120 per arm, for a total of 245 patients.

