5.5 STRATEGIES FOR RECRUITMENT AND RETENTION

Male and female participants above the age of 18 will be screened to reach target enrollment 174 patients over a period of 16 months. Participants presenting with pain due to a musculoskeletal injury will be screened and enrolled at four sites (Cedars Sinai Orthopedic Clinic, Medical Delivery Network, Cedars Sinai Pain Management Clinic, Medical College of Wisconsin). Patients will be identified and approached by their providers. The treating physicians will contact their patients during their clinic visits and assess the patient's willingness to be contacted about the research and the treating physician will document the patient's willingness to be contacted on the *CSMS Research Interest* letter. The Research Letter will be tailored to each clinical practice of the treating provider. Additionally, participating providers will distribute recruitment pamphlets to patients in clinic and/or through mail. Should the patient be interested in being contacted about the study, the study team will then approach the patient for

participation in the research either in person or over-the-phone. The patient will have the option to complete their consent forms on paper or electronically using the 21 CFR 11-compliant online platform, DocuSign. Every subject will be informed of the approximate time to complete the consent process. Consenting will be done with a research staff member either in-person or remotely via DocuSign to ensure the identity of the person signing the informed consent form is indeed the subject participating in the research study. A copy of the informed consent documents will be given to the participants for their records via their email or a physical hard copy. Participants who consent remotely will receive their study equipment through a secure FedEx package requiring a signature. Retention to the 60-day study for the intervention group will be managed using weekly reminders to complete survey protocols, as well as optional opt-in monitoring of compliance and health data via remote clinical and technical support staff. Participants will not receive monetary compensation for participating in this study.

Participants experiencing lower back pain will be oversampled to a minimum of 45 per arm in order to obtain sufficient sample size for testing the success of the TENS unit.

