6.2 MEASURES TO MINIMIZE BIAS: RANDOMIZATION AND BLINDING

Per the new protocol, participants will be randomized intervention or control until intervention and control groups each have 75 enrollees. In addition to these 150 participants, the group of 24 controls that were originally recruited without the TENS unit will remain accounted for in the supplementary analysis. There will be no blinding, as participants in the control group will be aware that they are missing components of the intervention as detailed in the consent form.

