7.2 PARTICIPANT DISCONTINUATION/WITHDRAWAL FROM THE STUDY

Participants are free to withdraw from participation in the study at any time upon request. An investigator may discontinue or withdraw a participant from the study for the following reasons:

- Pregnancy
- Significant study intervention non-compliance
- If any clinical adverse event (AE), laboratory abnormality, or other medical condition or situation occurs such that continued participation in the study would not be in the best interest of the participant
- Disease progression which requires discontinuation of the study intervention
- If the participant meets an exclusion criterion (either newly developed or not previously recognized) that precludes further study participation

The reason for participant discontinuation or withdrawal from the study will be recorded. Subjects who sign the informed consent form and receive the study intervention, and subsequently withdraw, or are withdrawn or discontinued from the study, will be replaced.

Participants will not be financially responsible for damage to, or loss of, equipment loaned to participants by investigators during this study.

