9.4.2 ANALYSIS OF THE PRIMARY EFFICACY ENDPOINT(S)

Statistical Analyses: Data for Aim 1 are repeated-measures data and will not support bivariate analysis by Pearson and/or Spearman correlations, as autocorrelation can cause transient or spurious relationships with high correlations for some periods and none for others. Similarly, for a linear regression model, this type of data may cause residuals for the same individual to be correlated. Therefore, we will employ linear mixed models featuring fixed effects and random effects (i.e. random intercepts) to account for within subject variation. We will also perform a differences-in-differences analysis comparing change between baseline and the end of the intervention to determine which strategy resulted in greater improvement in PF.

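### The sample size in section 9.2 (about 120 per arm, 245 in total) is twice what its own inputs give and contradicts the planned 75 + 75 randomised plus 24 early controls

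*Combined protocol and SAP*

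**What the plan says.** Section 9.2 targets a between-arm difference of 0.6 SD in the PROMIS physical function score. The figure it reaches is a "sample size requirement of approximately 120 per arm, for a total of 245 patients". The assumptions behind that figure are given just before it: 80% power, a 0.05 level and withdrawal of 25%. The section does not say whether the 0.05 is one- or two-sided, and it does not name the test behind the calculation.

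The enrolment plan is different elsewhere in the current text:

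- Synopsis (1.1): "174 English adults (75 intervention; 75 control with TENS; 24 control without TENS".
- Section 4.1: "In addition to these 24 controls, we will randomize 75 patients to receive the study intervention", with another 75 going to the active control.
- Section 5.5: patients "will be screened to reach target enrollment 174 patients over a period of 16 months".
- Section 6.2: "participants will be randomized intervention or control until intervention and control groups each have 75 enrollees", with the 24 early controls kept for a supplementary analysis.

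Section 7.2 adds that patients who receive the intervention "and subsequently withdraw, or are withdrawn or discontinued from the study, will be replaced". For the primary analysis, section 9.4.2 states that "we will employ linear mixed models featuring fixed effects and random effects (i.e. random intercepts" are specified, together with a comparison of change from baseline to the end of the intervention. Section 9.4.4 adds a TENS term to the mixed model and keeps the original power calculation, on the grounds that one term is added but so are 20 subjects.

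**The concern.** Two things do not fit. A standardised difference of 0.6 is fairly large, and 120 per arm is far more than 80% power should require, even after allowing for a quarter of patients withdrawing. Separately, section 9.2 presents its figure as a minimum, yet every section that describes enrolment plans well below it, and none gives the power of the planned size.

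Section 9.2 is the plan's only account of what the trial can detect. A reader who takes it at face value will conclude that the trial randomises about 61% of the patients it needs (150/245). A reader who recomputes it will find the reverse. Section 9.4.4 then rests the TENS-adjusted model on the same calculation.

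**Working it through.** **Inputs.** From 9.2: difference d = 0.6 SD, power 80%, level 0.05, withdrawal 25%. From 6.2: equal allocation, 75 per arm. From 1.1, 4.1 and 6.2: 24 early controls without TENS. Two-sided testing is assumed, because sidedness is not stated.

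**Attempt to reproduce the stated figure.**

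- Normal approximation: n = 2(1.960 + 0.842)²/0.6² = 43.6 evaluable per arm.
- Two-sample t-test: 44.6, so 45 evaluable per arm (power 0.804).
- Allowing for withdrawal: 45/0.75 = 60 randomised per arm, 120 in total.

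The stated per-arm figure is 120/60 = 2.0 times this. Other choices at 0.6 SD do not reach it either:

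| Variant | Evaluable per arm | Randomised per arm |
|---|---|---|
| One-sided 0.05, 80% power | 36 | 48 |
| Two-sided 0.05, 90% power | 60 | 80 |
| Two-sided 0.05, 95% power | 74 | 99 |

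In the other direction, 120 per arm with 25% loss leaves 90 evaluable. That gives 98% power at 0.6 SD, or 80% power at 0.42 SD.

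**Stated minimum against planned enrolment.** 75 + 75 = 150 randomised, and 150 + 24 = 174. Like for like, 245 − 150 = 95 short of the stated figure, and 120/75 = 1.6 per arm. Even counting all 174, the plan is 245 − 174 = 71 short. Against the recomputed requirement, 150 − 120 = 30 more than needed.

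**Power of the planned 75 versus 75** (two-sided t-test at one time point, as an approximation to the mixed model):

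| Evaluable per arm | Power at 0.6 SD | Difference with 80% power |
|---|---|---|
| 56 (75 × 0.75 = 56.25) | 88% | 0.53 SD |
| 75 (withdrawals fully replaced) | 95% | 0.46 SD |

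**The argument in 9.4.4.** The early controls number 24 in 1.1, 4.1 and 6.2, not 20. In the written model they are the only patients with TENS = 0, so they determine the TENS coefficient and leave the arm coefficient to the 75 versus 75 comparison. This was checked by generalised least squares with 10 PROMIS time points and compound symmetry. The within-patient correlation is not in the documents and was varied from 0.2 to 0.8. The standard error of the arm coefficient with 75 + 75 + 24 and the TENS term, divided by that with 75 + 75 and no TENS term, is 1.0000 with complete data or equal 25% dropout. It is at least 0.9998 with unequal dropout (35% versus 15%). The extra controls therefore offset nothing.

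**The case against.** The best defence is that section 9.2 names no test, and section 9.4.2 includes an analysis of change from baseline. If 0.6 is scaled to the SD of the raw score and the baseline-to-end correlation is zero, the change has variance 2 × (1 − 0) = 2 in SD² units. The requirement becomes 88.2, so 89 evaluable and 89/0.75 = 119 per arm, close to the stated figure. But 9.2 does not state this basis, and 9.4.2 expects one person's residuals to be correlated. At a correlation of 0.3 the need falls to 84 per arm, and at 0.5 it is back to 60. This may be where the figure came from. So may a total of 120 written as a per-arm number. The documents settle neither, and neither removes the conflict with 75 + 75.

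A second objection is that 9.3 and 9.4.4 can be read as keeping the early controls in the by-arm intention-to-treat comparison, making it 75 versus 99. With 25% loss (56 versus 74) that gives about 92% power at 0.6 SD, and 80% at 0.50 SD. Against that model, separating out TENS does have a price: the standard error of the arm effect rises by a factor of √(2/75)/√(1/75 + 1/99) = 1.067. This stands as a qualification. Sections 4.1 and 6.2 assign the 24 to a supplementary analysis, so 75 versus 75 is the comparison to power. The extra controls do not offset the added term on either reading.

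Two smaller cautions also stand. The figures for 75 evaluable per arm depend on how replacement under 7.2 works alongside the 75 enrollees in 6.2. And 9.4.4 does not say outright that its 20 subjects are the early controls, though no other group fits.

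**Conclusion.** The point holds. The stated inputs give 60 per arm and 120 in total, not about 120 per arm and 245. The stated minimum and the enrolment plan cannot both stand. The conclusion assumes a two-sided, single-time-point comparison of two means; one-sided testing moves the figure further from 120.

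The error lies in the stated figure and its justification, not in the number of patients: 75 per arm exceeds the 60 required for 0.6 SD. The power figures for the planned size are t-test approximations to the mixed model. It must be fixed because it is the sample-size statement for the primary endpoint, it conflicts with the enrolment figures in four other sections, and 9.4.4 depends on it.

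**What to change.** **Section 9.2.** Replace the stated requirement with: about 45 evaluable and 60 randomised per arm, 120 in total (two-sided 0.05). If another basis was used, state it with all its inputs, including any baseline-to-end correlation.

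Then add the power of the planned size: *By a two-sample t-test approximation to the mixed-model analysis, 75 versus 75 gives 88% power at 0.6 SD (80% at 0.53 SD) with 25% loss (56 per arm), and 95% (80% at 0.46 SD) if withdrawals are replaced to 75 evaluable per arm.* Keep the last clause only if replacement under 7.2 is meant to work that way.

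**Section 9.4.4.** Reconcile the 20 subjects with the 24 early controls given elsewhere, remove the argument that added subjects offset the added term, and refer to the restated 75 versus 75 power.

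**Cost.** Wording and restated figures only. No extra patients, visits or analyses.
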